3.1 Study Duration

This study will be conducted from 1 November 2018 through 31 December 2019 (13 months). This will allow sufficient time for study preparation (November 2018; 1 month), enrollment (approximately 3 months, starting December 1, 2018), follow-up (approximately 6 months from the time the last patient is consented), analysis (August 2019 – September 2019; 2 months), delivery of a final report to the Intermountain Healthcare Executive Leadership Team and co-authoring a manuscript for submission in a high-impact, peer-reviewed journal (October 2019 – December 2019; 2 months).

3.2 Number of Subjects

We aim to recruit 125 patients, expecting 20% attrition by the six-month follow-up, yielding about 100 patients for analysis (see *7.2 Sample Size and Power*).

3.3 Screening and Selection of Subjects

Subjects will be screened and recruited by Research Coordinators with CITI/HIPAA training. These coordinators will be trained in advance by Drs. [name] and [name], on how to instruct patients of proper usage of their device, how to effectively interact with subjects, the questions that may be posed, how patients should interpret feedback from the devices/cellphones, etc. [name] will also consult with the providers so that they understand the questions that may be asked by the patients and how to provide best care practices.

If a patient agrees to participate, a consent form will be electronically signed using REDCap. Participants will receive a paper copy of the consent containing all relevant and study pertaining information including important contact information. The subject will then be randomized into a study group and given the appropriate device by a Research Coordinator. Each patient will download the mobile apps relevant to their group, so their data can be tracked and transmitted by the study team.

- Group #1 will download the Dexcom G6 and Clarity apps
- Group #2 will download the Contour Next ONE Diabetes application.
- Both groups will also use REDCap to complete the end of study survey (**Appendix A**).

All devices will be registered prior to study startup and will be matched to a deidentified subject identifier (e.g. Subject_001). The coordinators will answer any study related questions that the patients may have before and during the study along with the Reimagine Primary Care clinicians who have agreed to participate as collaborators during the patient's regular appointments. Before patient's leave the clinic, (or ± 2 days) a blood draw will be conducted at the Reimagine site by a certified phlebotomist or approved healthcare provider to collect initial HbA1c level.

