Randomization will be assigned *a priori* using a random number generator from Microsoft Excel. Sub-Investigator will then transcribe these numbers and order them individually in concealed envelopes and present them to the Research Coordinators to ensure the CRC is blinded. At time of consent the Research Coordinator will hand the patient the earliest numbered envelope to randomize. . Patients in both randomized groups will be given the devices and one month supplies to ensure compliance with the protocol. The Study Coordinator and patient will exchange contact information so that the CRC may resupply the patient with necessary equipment at the end of their month supply. The CRC may meet the patient at their Reimagine Care Clinic or off site for patient convenience. All patients are expected to participate for six months, which is near the minimum duration sufficient to measure clinically meaningful changes in hemoglobin A1c related to gradual behavioral changes (e.g., diet, exercise, insulin administration). Further, each patient will complete 2 mandatory blood draws and one elective blood draw at their designated Reimagine Care Clinic to evaluate HbA1c level changes over the course of the study. Baseline HbA1c must be completed on day of enrollment (± 2 days) which Intermountain Healthcare may choose to cover if not paid for by patient's SOC. An elective blood draw will be considered for data if completed at 3 months (± 1 week) and a third required blood draw upon study completion (± 2 weeks) which the study may also choose to cover if not SOC. 2 weeks from 180 enrollment) which the study may pay for if not covered by patient's SOC. We postulate that those that have a more consistent interstitial glucose profile (which avoid the high peak to valley swings), will have a more pronounced difference in pre and post HbA1c levels. Specific Aim #1 above will help our team understand the relationship between interstitial glucose and HbA1c, along with other outcomes of interest which include weight loss, alterations in diet, change in physical activity, etc.

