7.1 Statistical Considerations

The primary analysis (Aim 1a) will measure the intervention effect on the patient-level six-month absolute reduction in mean HbA1c. Since not all patients will have their final HbA1c test at six months exactly, we will estimate each patient's six-month reduction in HbA1c by interpolating/extrapolating from their assessments, given that their HbA1c levels were assessed on at least two occasions: baseline, and >3 months post baseline. Then, among patients with a sufficient number of occasions of HbA1c assessments, we will estimate their sixmonth HbA1c using generalized linear mixed models with patient-level random slopes and intercepts, with appropriate link function and distributional family [8]. The quantitative secondary analyses (Aims 1b-e, 2a-b) will use outcomes related to the longitudinal change in various metrics of glycemic variability (MAGE, C_v , range) as well as the frequency of hypoglycemic events, healthcare utilization, and cost. The secondary analyses will also use longitudinal data analysis to assess whether there is a significant reduction in glycemic variability over six months (Aims 1b-d) among those randomized to CGM, whether there is a significant reduction in hypoglycemic events over six months (Aim 1e) among those randomized to CGM, and to assess whether overall healthcare utilization and costs differ between randomized groups [9]. Accordingly, specific aims 1b-e will rely heavily on longitudinal data analysis within a multilevel/hierarchical framework [10], specifically using generalized linear mixed models. In the sensitivity analyses, provider variability will be accounted for using three-level (provider, patient, occasion), quasi-Bayesian generalized linear mixed models [11]. Finally, the sensitivity analyses exploring HTE will use generalized additive models (GAM) to identify subgroups of patients for whom CGM is likely to have a differential effect [12-13].

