12.0 APPENDIX A

This section provides the questions which will be entered into REDCap and patients asked to complete at the end of the CGM study. There will be branching logic used based on the specific group assigned.

- 1. Which group were you assigned to?**
 - a. Group 1 (Dexcom G6)
 - b. Group 2 (ContourNext One)
- 2. What was the main reason that you signed up for this trial? _____.**
- 3. What was your biggest concern when you considered participating in this trial? _____.**
- 4. Were you initially disappointed with your group assignment?**
 - a. Yes
 - b. No

4b. Why were you disappointed with your group assignment? _____.
- 5. (For Group 1 participants): Did the Dexcom G6 impact your glucose management? For example, did it change your diet?**
 - a. Yes
 - b. No
- 6. (For Group 1 participants): Did the Dexcom G6 impact your glucose management? For example, did it change your exercise regimen?**
 - a. Yes
 - b. No
- 7. How did Dexcom G6 impact your glucose management? _____.**
- 8. (For Group 1 and 2 participants): On a scale of 1-5, where 1 is not helpful and 5 is extremely helpful, how would you rate the device?**
- 9. (For Group 1 and 2 participants): On a scale of 1-5, where 1 is extremely poor and 5 is extremely healthy, how would you rate your health BEFORE starting this study?**
- 10. (For Group 1 and 2 participants): On a scale of 1-5, where 1 is extremely poor and 5 was extremely healthy, how would you rate your health AFTER starting this study was completed?**
- 11. (For Group 2 participants): Did the ContourNext One impact your glucose management? For example, did it change your diet?**
- 12. (For Group 2 participants): Did the ContourNext One impact your glucose management? For example, did it change your exercise regimen?**
- 13. How did the ContourNext One impact your glucose management? _____.**
- 14. Did your glucose levels decrease between the initial enrollment and the end of the study? (Suggest inserting this filter question.)**
 - a. They increased
 - b. The decreased

c. No change

15. Would you be willing to participate in future Intermountain pilots in your primary care clinic? a.

Yes

b. No

16. General Comments. In the space provided, please feel free to add any other comments regarding your participation in this study. _____.

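### The baseline HbA1c may be drawn up to 2 days after the patient knows the arm, yet the primary analysis requires it: a small, avoidable route to arm-related exclusion

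*Combined protocol and SAP*

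**What the plan says.** Section 3.0 places allocation at consent: "At time of consent the Research Coordinator will hand the patient the earliest numbered envelope to randomize". Section 3.3 gives the same order. Once the consent form is signed, "The subject will then be randomized into a study group and given the appropriate device by a Research Coordinator"; the apps follow, and the section ends with the blood draw: "Before patient's leave the clinic, (or ± 2 days) a blood draw will be conducted at the Reimagine site". Section 3.0 states the same window: "Baseline HbA1c must be completed on day of enrollment (± 2 days"). Neither section requires the draw to come before the envelope is opened.

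Section 7.1 estimates each patient's six-month reduction "given that their HbA1c levels were assessed on at least two occasions: baseline, and >3 months post baseline", and fits the mixed model "among patients with a sufficient number of occasions of HbA1c assessments". It does not define baseline itself; section 3.0 uses the word for the enrollment draw.

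A different, earlier HbA1c decides eligibility: section 3.0 uses the most recent level, with no stated limit on its age. Section 4.2 collects past HbA1c results. Neither is linked to the primary analysis. The documents describe no fallback baseline, no analysis set of all randomized patients and no missing-data method for a patient without a baseline.

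**The concern.** The primary endpoint is a change score, and its first half may be collected after allocation is known. The two devices differ visibly, so the patient cannot be blinded. A patient who draws the finger-prick envelope may leave, comply with the protocol up to that point, and not come back for the draw. As section 7.1 is written, that patient then has no six-month change and is not compared.

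If this happens more in one arm, and those patients would have changed differently from the rest, the analyzed groups are no longer the randomized groups. Some features of the plan make an arm-related no-show plausible. Controls continue their existing regimen (section 3.0), are not compensated and return the meter (section 9.2). Payment for a draw outside standard care is optional (section 3.0). The exit survey in Appendix A also asks: "Were you initially disappointed with your group assignment".

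**Working it through.** **1. The plan's own figures.** Section 7.2 gives 125 enrolled, 20% attrition, about 100 analyzed, and more than 80% power at a standardized difference above 0.8, with an example of a difference of -1 and an SD of change of 1.25. The alpha level and allocation ratio are not stated; 0.05 two-sided and 1:1 are assumed here.
- Enrollment: 100 / (1 - 0.20) = 125. Reproduced.
- Standardized difference: 1 / 1.25 = 0.8. Reproduced.
- Power with 50 per arm (normal approximation): 0.8 / √(2/50) = 4.0, and Φ(4.0 - 1.96) = 97.9%. The noncentral t gives 97.7%. For the planned Wilcoxon test, relative efficiency 3/π gives 97.4% and the worst case of 0.864 gives 96.1%. All satisfy the stated inequality.

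**2. The sequence.**

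| Step | Section | Arm known? |
|---|---|---|
| Most recent HbA1c used for eligibility | 3.0 | No |
| Consent | 3.3, 4.1 | No |
| Envelope handed over | 3.0 | Yes |
| Device and apps | 3.3 | Yes |
| Baseline draw, before leaving or in the later part of the window | 3.0, 3.3 | Yes |
| Final draw | 3.0 | Yes |
| Entry to primary analysis: needs baseline and a value beyond 3 months | 7.1 | - |

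The window runs both ways, so a draw before allocation is also allowed. The exposed patients are those not drawn before they leave.

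**3. Size of the effect, on assumed inputs.** Let m be the excess share of one arm lost among patients who would otherwise be analyzed, and D the difference in mean HbA1c change between lost and retained patients. The full arm's mean is (1 - m) × retained + m × lost, so the retained mean is off by

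bias = m × D.

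With 50 patients in the intact arm, 50(1 - m) in the other and SD 1.25, SE = 1.25 × √(1/50 + 1/(50(1 - m))). The two-sided type I error is Φ(-1.96 + bias/SE) + Φ(-1.96 - bias/SE). This is a normal approximation for a comparison of means, used as a guide to the planned rank test.

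| m | n in reduced arm | Bias, D = 0.5 | Type I | Bias, D = 1.0 | Type I | Power at 0.8 (t, fewer patients only) |
|---|---|---|---|---|---|---|
| 2% | 49 | 0.010 | 5.02% | 0.020 | 5.07% | 97.6% |
| 5% | 47.5 | 0.025 | 5.11% | 0.050 | 5.45% | 97.4% |
| 10% | 45 | 0.050 | 5.44% | 0.100 | 6.75% | 97.1% |
| 20% | 40 | 0.100 | 6.64% | 0.200 | 11.73% | 96.2% |

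Worked example, m = 10% and D = 1.0: bias 0.10; SE = 1.25 × √(1/50 + 1/45) = 0.257; bias/SE = 0.389; Φ(-1.571) + Φ(-2.349) = 0.058 + 0.009 = 6.75%.

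For m of 5-10% and D of 0.5-1.0, the bias is 0.025-0.10 points, or 2.5-10% of the example difference of 1. The direction is unknown, since the documents do not say whether lost patients would do better or worse.

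**The case against.** The case against giving this much weight is substantial, and most of it stands.

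- **The loss is partly repairable.** A reader might infer that a missed baseline cannot be recovered and that no analysis could rescue the comparison. The documents do not support that. Eligibility rests on an HbA1c that already exists, and past results are collected, so a pre-randomization value is available as a fallback baseline or covariate. The repair is only partial: no limit is set on the age of that value, section 5.2 ends record access for patients who withdraw and refuse further collection, and the plan does not name the value for this use.
- **Few patients are exposed.** The draw is mandatory and a draw before leaving is the default.
- **Many of those patients would be lost anyway.** Someone who skips a draw due within 2 days may well miss the final one, and section 7.1 then excludes that patient whatever the order. The draw order matters only for those who miss the baseline and later return. The requirement for a value beyond 3 months, with 20% expected attrition (25 of 125), is probably the larger source of exclusion under the same rule, and reordering the draw does not touch it.
- **The survey question is weak evidence.** It is put to both arms at study end, to patients who stayed. It shows that the sponsor foresaw disappointment, not that disappointed controls leave before baseline.
- **The rates are assumed.** Nothing in the documents supports 5-10% over any other figure.

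What remains is the gap itself: the text permits the late draw, makes the primary analysis depend on it, and provides no fallback.

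**Conclusion.** The point holds as a small, avoidable weakness of design. The documents allow the baseline draw after allocation is known and exclude patients without a baseline from the primary estimate, so exclusion can depend on arm. On the assumed inputs (50 per arm, SD 1.25, 5-10% excess loss in one arm, a difference of 0.5-1.0 points) the bias is about 0.025-0.10 HbA1c points and the type I error about 5.1-6.8%. It grows beyond that only if missed baselines are common and one-sided.

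Three further readings go too far. The sample size is not put at risk: power at a standardized difference of 0.8 stays at 96% or more after the losses considered. Nothing here shows that up to two days with a device changes HbA1c, and the point does not need it. Nor do the documents show that such losses will occur, only that the plan leaves room for them. Confidence is high for the sequence and low for the size.

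**What to change.** - **Sections 3.0 and 3.3:** draw the baseline HbA1c after consent and before the envelope is opened. Replace the two-sided 2-day window with: on the day of randomization, before allocation, or up to 2 days before. If blood cannot be drawn at the consent visit, open the envelope only when the patient returns for the draw.
- **Section 7.1:** name the last pre-randomization HbA1c as the baseline if the study draw is missing (for example, a failed sample), and report missing baselines by arm.

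The draw, site and staff are already planned, and section 4.1 already lets a patient come back to finish consenting, so this changes wording and visit order only. The cost is an occasional return visit before randomization and a few consented patients who are never randomized. Losing them before allocation cannot bias the comparison. Exclusion for a missing final value remains and needs its own missing-data provision.

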3.3.1 Inclusion Criteria

- Type 1 or type 2 diabetes mellitus with a HbA1c $\geq 6.5\%$
- Patients that are currently managing their glucose levels for diabetes with a glucose meter (or will be prescribed one by their healthcare provider)
- Patients that are treated within the four Reimagine Primary Care clinics (Cottonwood Family Medicine, Cottonwood Senior, Avenues Internal Medicine, and Holladay Internal Medicine).
- Patients 18-80 years of age

3.3.2 Exclusion Criteria

- Patients that are not managing their glucose levels for diabetes (and not advised to use a glucose monitor by their physician)
- Patients that are not treated within the four Reimagine Primary Care clinics
- Patients less than 18 years of age, and 81 years of age and older
- Patients with a diagnosis of dementia
- If the patient is currently using a Continuous Glucose Monitor
- Patients with previous hospitalization for hypoglycemia within the last 18 months
- No access to a mobile phone to download the Dexcom or Contour Next applications
- Patients who are pregnant or planning to become pregnant over the course of their six-month participation

4.0 STUDY PROCEDURES

4.1 Informed Consent

Patients that meet eligibility criteria and agree to participate will be considered for the study. These patients will be identified in advance through Tableau/PowerChart or on the day of the appointment in the clinic. Patients may be approached with a brochure and ICF in the lobby prior to their appointment but will not be consented until their clinic visit is completed as to not disrupt clinic flow. If approved by the patient's provider, they may also be contacted by phone from a Research Coordinator (using IRB approved phone script) to schedule a time to meet at their RPC Clinic for recruiting. A consent that is approved by the Intermountain

Healthcare Institutional Review Board (IRB) will be obtained prior to study inclusion, signed electronically in REDCap by the subject or his/her legally authorized representative, in accordance with applicable regulations.

The informed consent process will occur at a Reimagine Primary Care facility. Research Coordinators, the Principal Investigator, Co-Investigators, or an appropriately delegated member of the study team may administer the informed consent process.

Patients will be given as much time as they need to consider participation, ask questions, and obtain satisfactory answers to their questions. If a patient cannot consent due to time restraints or other conflicting obligations it will be allowable for the patient to return to the Reimagine Care Clinic to meet with the Research Coordinator to finish consenting at a later time. Patients who agree to participate, will receive a unique study identifier. Lastly, since patients are signing electronically, they will be provided a handout that matches their exact consent form to take home which will have information on who to call with questions, comments or concerns.

4.2 Methods

Patients will be screened for eligibility per Inclusion and Exclusion criteria (See Sections 3.3.1 and 3.3.2 respectively) and consented as described in Section 4.1.

The following information will be obtained from each subject's medical records, and/or during procedures, treatments, study-specific visits, and/or follow-up visits that are generally part of their usual or specialized care:

- Patient's ID number (EMPI)
- General demographic information (age, gender, height, weight, race, ethnicity)
- Patient's contact information (email, home address, and phone)
- Health history (personal health history, previous laboratory and glucose test results, medications, healthcare utilization and cost data)
- Current medications/medication history
- Glucose levels and historical A1c reports

Group #2 data will be transmitted from the Contour Next One device to the Contour mobile app via Bluetooth. Should this process fail, a contingency plan has been devised for patients to manually record their readings in an online REDCap form or provide their readings to their Research Coordinator who will properly store the data. Patients in the intervention group will have their data automatically uploaded via the Dexcom G6 app where it will then be obtained by Intermountain Healthcare researchers. No protected health information will be shared with those outside of this research study unless approved by the IRB. Coordinators will check in with the patients on a monthly basis (or more frequently for non-compliance) to ensure proper data entry and to answer any questions (if necessary).

4.3 Risks

This study is low risk. The study uses FDA approved devices that are commercially-available to track glucose monitoring. The Intervention Group should experience less pain than the standard of care since they will not have daily finger pricks, and The Control Group is the current standard of care. As with all studies that involve data, there is always a risk that this could be shared, however, study-related information will be stored within Intermountain's system and applications that have been reviewed and approved by cybersecurity. Further, by using study ID number (e.g. Subject_001) rather than referring to PHI, we will minimize the risk of incidental disclosure.

The Dexcom G6 is a pressure sensitive acrylic adhesive coated on top of a polyester spunlace fabric. The plastic housing is attached to the patch by direct pressure and heat. There is no latex or bovine components in the adhesive however, if the patient has a severe acrylic or polyester allergy it is possible they may experience skin irritation or topical allergic reactions at the site of which sensor was applied.

4.4 Benefits

Patients enrolled in this study may benefit by utilizing a new FDA-approved device which will provide real-time data on their blood glucose levels (Intervention Group). CGM may empower patients to better manage their diabetes, potentially resulting in better stabilized blood glucose levels, reduced patient costs and burden of care, as well as potentially reducing the hazard of development of diabetic complications. Additionally, data collected in this study might be used to improve clinical/operational decisions, potentially yielding a more efficient and cost-effective care process model for high-risk patients.

